F. Criteria For Assigning Treatment Failure Status During Double-blind Treatment Period (weeks 7-24)

Treatment failure status will be defined as the occurrence of one or more of the following:

At-home measurements: *

1. PREbronchodilator PEF $\leq 65\%$ of baseline on any 2 of 3 consecutive scheduled measurements.
Baseline is defined as the average prebronchodilator AM PEF value recorded during the last two weeks of the run-in (weeks 5 and 6).
 2. POSTbronchodilator AM PEF $\leq 80\%$ of baseline.
For postbronchodilator AM PEF value, subject may take ≥ 6 puffs of albuterol within 1 hour (2-4 puffs every 20 minutes).
Baseline is defined as the average prebronchodilator AM PEF value recorded during the last two weeks of the run-in (weeks 5 and 6).
 3. An increase in PRN albuterol use of 8 puffs per 24 hours over baseline use for a period of 48 hrs or ≥ 16 puffs/24 hrs for 48 hrs.
Baseline is defined as average daily use during the last two weeks of the run-in (weeks 5 and 6).
- * Patients will be instructed to contact the ACRN study site immediately should any of these events occur.

In-clinic measurements:

1. POSTbronchodilator $FEV_1 \leq 80\%$ of the baseline POSTbronchodilator value obtained at Visit 4. All values obtained one hour post-salmeterol (single blind).

2. PREbronchodilator FEV₁ values on 2 consecutive sets of spirometric determinations which are $\leq 80\%$ of the baseline PREbronchodilator value obtained at Visit 4. This would involve the following comparisons:

Visit 6 and Visit 5
Visit 7 and Visit 6
Visit 8 and Visit 7
Visit 9 and Visit 8
Visit 10 and Visit 9
Visit 11 and Visit 10

ADDENDUM: As an addendum to these criteria, the subject will also be a treatment failure if the following set of circumstances occurs:

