2. If patients meet criteria for treatment failure status, their dose of inhaled corticosteroids will be increased to the dose they were receiving at visit 4 (800 $\mu\text{g}/\text{day}$) delivered by an open-label inhaler. Study inhalers of corticosteroids (or its placebo) will be returned to the clinical center. If they meet the criteria detailed in Section VI, they will be treated with appropriate rescue algorithms for an asthma exacerbation. Study inhalers of salmeterol (or placebo) will be continued unless the physician can document that treatment failure status was causally related to taking this medication. They will continue to participate in the study until its termination (intent-to-treat analysis), but no further reductions in inhaled corticosteroid dose will be attempted during this time period. For safety reasons, all subjects will be seen within one week ($\pm 3\text{d}$) from the day they were categorized as achieving treatment failure status. Following this "safety" visit, subsequent protocol visits will continue in accordance with the visit schedule established at Visit 1 (see SOCS/SLIC MOP for details concerning possible replacement of scheduled protocol visits with treatment failure related visits).

IV. OUTCOME VARIABLES

The primary outcome variable will be the time to treatment failure. It will be evaluated using a Kaplan-Meier survival analysis. Secondary outcome indicators will include comparisons of FEV₁, mean peak flow variability (PM-AM peak flow difference normalized by the average of the AM and PM peak flow), methacholine airway responsiveness following premedication with salmeterol (evaluation of bronchoprotective effect), asthma symptom scores, quality of life, and rescue medication use at visits 5-11 to those obtained at visit 4.

Daily data obtained from post-randomization diary cards will be summarized and analyzed as averages. Because subjects are instructed to withhold their study salmeterol (or placebo) for 12 hours prior to a visit, the affected peak flow values will be excluded.

V. PROTOCOL

A. Subjects

1. **Sample size.** This trial has a target sample size of 150 randomized patients, with 20 in Group A, 65 in Group B, and 65 in Group C. See section X.F for the derivation of this sample size.

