VI. ASTHMA EXACERBATIONS

A. Definition

During the course of the study, patients may experience an exacerbation of asthma. An exacerbation of asthma is characterized by an increase in symptoms of cough, chest tightness, and wheezing and it is generally associated with a fall in PEF. It is recognized, however, that the PEF may be improved by use of a bronchodilator and that increased bronchodilator use may, in this case, be more reflective of the exacerbation than PEF. An exacerbation may be brief and self-limited, or it may be of sufficient severity as to warrant documentation as a significant asthma exacerbation. Although any increase in symptoms or changes in PEF should be carefully monitored by the patient, the clinic coordinator, and the physician, alterations in asthma stability will be considered as constituting a significant asthma exacerbation when PEF does not increase to > 65% of reference levels, or symptoms are not satisfactorily relieved, after the first 60 minutes of rescue beta agonist (albuterol) use. Albuterol may be used at a dose of 2-4 puffs every 20 minutes during this one hour time period. For the SLIC protocol, the reference point for PEF comparisons will be as follows:

During run-in period (weeks 1 – 6): Weeks 1-2: Predicted PEF obtained from spirometry software at Visit 1

Weeks 3-6: Mean value of AM prebronchodilator PEF recorded during the first 2 weeks of the run-in (weeks 1 and 2)

During double-blind treatment (weeks 7 – 24): Mean value of AM prebronchodilator PEF recorded during the last 2 weeks of the run-in period (weeks 5 and 6)

In addition, a significant asthma exacerbation will be identified if patients have a significant increase in symptoms associated with either:

An increase in "as needed" β -agonist use of ≥ 8 puffs per 24 hours over baseline use for a period of 48 hours,

Baseline defined during run-in period: Average daily use during the first two weeks of the run-in period.

Baseline defined during double-blind period: Average daily use during the last two weeks of the run-in period.

or

Use of ≥ 16 puffs of "as needed" β -agonist per 24 hours for a period of 48 hours.

Once a significant asthma exacerbation has occurred, the patient should contact the clinic coordinator and/or be evaluated at the study site or the nearest medical emergency facility as quickly as possible.

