Trial triamcinolone or placebo will be stopped during exacerbations, and open label triamcinolone acetonide [400 μg (4 puffs) BID] restarted unless the treating physician considers it appropriate to suspend such therapy until the exacerbation resolves. This reinstatement of triamcinolone will occur when the exacerbation has resolved at the discretion of the investigator. A record of all medications, dosages, and frequency of occurrence will be kept during exacerbations. Additional visits and procedures will be scheduled according to guidelines for treatment failure visits (Section E, Visit Structures).

B. Rescue Algorithms

Rescue algorithms will be applied in cases where postbronchodilator PEF falls \geq 35% below baseline and is not improved to $>$ 65% of reference level within 48 hours after increasing as needed albuterol use. Rescue algorithms are based on recommendations from the NAEP Guidelines for the Diagnosis and Management of Asthma (NHLBI Publication No. 91-3042, 1991). Albuterol and oral prednisone are the principal medications for rescue management, therefore, patients will be instructed in their use for home management and supplies of both will be provided throughout the study. For severe acute episodes of asthma, treatment will be administered according to the best medical judgment of the treating physician.

1) Home Care:

Asthma exacerbations will be recognized by an increase in symptoms and by a corresponding drop in PEF below reference level. Patients will be educated to recognize exacerbations as early as possible to facilitate prompt treatment and to lessen morbidity.

- Patients who recognize increased symptoms and/or a fall in PEF to \leq 65% reference level will use albuterol by MDI, 2-4 puffs every 20 min up to 60 min if needed, and then every 4 hours, or less, if needed. Patients will be instructed to use the as needed inhaler for treatment.
- If the PEF does not increase to $>$ 65% reference level or if symptoms are not improved after the first 60 min of therapy, the patient should contact the investigator, their primary physician or seek care in the emergency department. This sequence of events constitutes a significant asthma exacerbation.
- Failure of albuterol to control or maintain PEF $>$ 65% reference level may necessitate the use of corticosteroids (see below).

2) Physician's Office or Emergency Room Treatment:

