- An increase in "as needed" β -agonist use of ≥ 8 puffs per 24 hours over baseline use (baseline defined as average daily use over last 2 weeks of run-in period) for a period of 48 hours, or
- Use of ≥ 16 puffs of "as needed" β -agonist per 24 hours for a period of 48 hours.
- When PEF falls to $< 50\%$ reference level despite albuterol treatment.

The dose of prednisone used during an acute exacerbation shall consist of 60 mg as a single dose every day for 3 days, followed by a 10 mg/day taper over the next 5 days. The decision to initiate or to continue a course of prednisone beyond 8 days is left to the discretion of the physician.

C. Adjustment of Trial Medications During Asthma Exacerbations

Trial salmeterol or placebo will be continued during exacerbations which occur during the double-blind treatment period, unless the treating physician considers it appropriate to suspend such therapy until the exacerbation resolves. Reinstitution of trial medications (salmeterol or placebo) will occur when the exacerbation has resolved at the discretion of the investigator. Trial triamcinolone or placebo will be stopped during exacerbations, and open label triamcinolone acetate [400 μ g (4 puffs) BID] restarted unless the treating physician considers it appropriate to suspend such therapy until the exacerbation resolves. Reinstitution of open-label triamcinolone will occur when the exacerbation has resolved at the discretion of the investigator. A record of all medications, dosages, and frequency of occurrence will be kept during exacerbations. By definition, the development of a significant asthma exacerbation in SLIC constitutes treatment failure status.

Patients developing asthma exacerbation during the *run-in period* will be removed from the study. Once the exacerbation has been resolved, the patient may be considered for re-enrollment, starting again at Visit 1 and undergoing randomization into either SOCS or SLIC as previously described.

D. Study Center Visits Following Exacerbations

For safety reasons, all subjects will be seen within one week ($\pm 3d$) from the date of the exacerbation. Following this "safety" visit, subsequent protocol visits will continue in accordance with the visit schedule established at Visit 1 (see SOCS/SLIC MOP for details concerning possible replacement of scheduled protocol visits with treatment failure related visits).

E. Criteria for Discontinuing Patients Due to Asthma Exacerbations

1. Treatment Failure Status

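### Section VI.B makes the rescue algorithms wait 48 hours for PEF recovery, while VI.A and VI.B.1 escalate at the same PEF level after 60 minutes

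*Protocol*

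**What the plan says.** Three parts of Section VI bear on when rescue treatment escalates.

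- **VI.B, opening sentence.** The rescue algorithms apply when postbronchodilator PEF is 35% or more below baseline and has not improved to above 65% "of reference level within 48 hours after increasing as needed albuterol use". Symptoms are not mentioned.
- **VI.A, Definition.** A significant exacerbation exists when PEF does not exceed 65% of reference "or symptoms are not satisfactorily relieved, after the first 60 minutes of rescue beta agonist (albuterol) use". The patient is then to contact the coordinator or be evaluated without delay.
- **VI.B.1, Home Care.** This is the first of the rescue algorithms. It covers "Patients who recognize increased symptoms and/or a fall in PEF to" 65% of reference or lower and starts albuterol at once. If PEF stays at or below 65%, or "if symptoms are not improved after the first 60 min of therapy, the patient should contact the investigator", a primary physician or an emergency department. It adds: "This sequence of events constitutes a significant asthma exacerbation".

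Section III.G.2, the instructions for Visits 5 to 10 and the Treatment Failure Visit all carry the same referral: "If they meet the criteria detailed in Section VI, they will be treated with appropriate rescue algorithms for an asthma exacerbation".

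**The concern.** Section VI gives two times for one clinical situation. The longer one stands in the sentence that states when the algorithms as a whole come into use, and the shorter one stands inside the first of those algorithms. Staff sent to Section VI to decide on rescue treatment can find either.

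The trial reduces and then stops inhaled corticosteroids in two of three groups. Section VII.B.1 expects exacerbations and counts the rescue algorithms among its safety nets. A clinician who took the opening sentence of VI.B as the criterion could judge it unmet because 48 hours had not passed, although VI.A and VI.B.1 already class the event as a significant exacerbation. Centers could therefore differ in when they move beyond albuterol. A symptomatic patient with preserved PEF would fall outside the opening sentence altogether, and VI.A itself warns that bronchodilator use can improve PEF during an exacerbation.

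**Working it through.** No sample size, power or alpha figure is involved. The check is whether the rules describe the same event and whether they can be read as successive stages.

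**1. Same PEF level.** A fall of 35% leaves 100% − 35% = 65% of baseline. VI.A and VI.B.1 use 65% of reference.

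**2. Same denominator in weeks 7–24.** The VI.A reference for double-blind treatment is the mean AM prebronchodilator PEF of weeks 5 and 6. The III.F baseline for PEF is that same mean. VI.B does not define its own baseline, so the equality assumes that it uses the III.F one.

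**3. Different times.**

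| Source | PEF condition | Symptoms alone count? | Time allowed on albuterol |
|---|---|---|---|
| VI.B, opening sentence | At least 35% below baseline, not above 65% of reference | No | 48 hours |
| VI.A | Not above 65% of reference | Yes | 60 minutes |
| VI.B.1 | Not above 65% of reference | Yes | 60 minutes |

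48 hours × 60 = 2,880 minutes, and 2,880 / 60 = 48, so the times differ 48-fold.

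**4. Not successive stages.** The opening sentence presupposes that albuterol has already been increased, so the conflict concerns escalation and not first-line albuterol. It governs the whole set of algorithms, including VI.B.1, which begins at the initial fall and has already sent the patient for medical help at 60 minutes. VI.B.2 also runs on steps of 60 minutes and 4 hours. VI.A explains that the algorithms exist because lesser changes can come before severe ones, and a 48-hour entry condition does not fit that purpose.

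**5. Where 48 hours otherwise appears in Section VI.** It belongs to the albuterol-use criteria in VI.A and VI.B.3: at least 8 puffs per 24 hours over baseline, or at least 16 puffs "per 24 hours for a period of 48 hours". Those measure sustained use, not PEF recovery. The period may have been carried over from there, but the protocol does not say so.

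**6. Referrals to Section VI.** III.G.2 (1) + Visits 5, 6, 7, 8, 9 and 10 (6) + Treatment Failure Visit (1) = 8.

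**The case against.** The best defense is that the operative steps agree with each other and only an introductory sentence is out of line. VI.A, VI.B.1 and VI.B.2 all use the short clock, and no numbered step tells anyone to wait 48 hours for PEF to recover. The referrals most naturally point to the definition in VI.A. They repeat one standard paragraph, and they concern patients already found to be treatment failures at a visit, so the count of eight adds little weight. The opening sentence does not say that rescue applies only after 48 hours, so it could be read as one sufficient condition among several. VI.B.1 already covers symptomatic patients.

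Other safeguards also act sooner:

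- III.F makes a postbronchodilator AM PEF at or below 80% of baseline a treatment failure, assessed with albuterol given within one hour. An AM value at or below 65% of that baseline already meets this. For the at-home criteria, "Patients will be instructed to contact the ACRN study site immediately should any of these events occur".
- VI.B.3 allows prednisone once treatment failure status is reached, and when PEF is below 50% of reference despite albuterol. Neither indication has a 48-hour wait.
- The scheduled telephone calls direct patients who meet failure criteria to attend within 24 hours.
- Physician judgment is preserved in VI.A and VI.B.

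Much of this stands as a limit on practical risk, and the repeated referrals are indeed one paragraph. It does not remove the contradiction. The sentence reads as the entry condition for the whole set of algorithms, so treating it as one optional trigger is strained. The safeguards do not tell staff which time applies. The below-50% indication leaves out PEF between 50% and 65%, and the judgment clause in VI.B is worded for severe acute episodes.

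**Conclusion.** The concern holds. Section VI states two escalation times at one PEF level, 48 hours and 60 minutes, and its opening rescue sentence omits symptoms that VI.A and VI.B.1 act on. The identity of PEF level is exact for weeks 7–24 if VI.B uses the III.F baseline. During the run-in VI.B gives no baseline to compare with the VI.A reference.

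The practical risk is limited, and the number of patients who might be affected cannot be derived from the protocol. The definition of treatment failure does not rest on the 48-hour sentence, so the primary endpoint definition, the analysis and the sample size are unaffected. A wrong time threshold in a safety instruction of a steroid-withdrawal trial should still be corrected. Confidence in the textual contradiction is high.

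**What to change.** Reword the opening sentence of VI.B to say that the rescue algorithms apply when symptoms increase and/or PEF is at or below 65% of reference, with escalation if there is no response after the first 60 minutes of albuterol, as VI.A and VI.B.1 already provide. Using the term reference throughout also removes the undefined baseline. Keep 48 hours only for the sustained albuterol-use criteria in VI.A and VI.B.3. The medical leads should confirm the wording.

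The cost is one sentence and a short memo to the sites. Section III.F, the endpoint, the analysis and the sample size need no change.

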10. Inability, in the opinion of the investigator or clinic coordinator, to coordinate use of a metered dose inhaler (MDI).
11. Changes of ischemic heart disease or arrhythmia on screening ECG (not excluded for occasional, $\leq 3/\text{min}$, atrial or ventricular premature contractions, or clinically insignificant sinus bradycardia).
12. Pregnancy. If potentially able to bear children, not using an acceptable form of birth control (see ACRN MOP, Appendix One).

13. Inability, as evidenced through biological quality control testing, to correctly use an AirWatch™ device for recording peak flow measurements.

C. Inclusion Criteria For Randomization (at Visit 4)

1. Prebronchodilator FEV₁ • 80% of predicted.
2. If FEV₁ is > 80% predicted, average variability $\frac{PM - AM}{1/2 (PM+AM)}$ in PEF > 20% during the final two weeks of the run-in period (weeks 5 and 6).
3. Ability of the subject to measure his/her AM and PM PEF on schedule using the AirWatch device, to appropriately mark the measurements using the post-medication marker, and to accurately transcribe the PEF measurements onto his/her diary cards at least 85% of the time during the last two weeks of the run-in.

D. Exclusion Criteria For Randomization (at Visit 4)

1. Significant exacerbation of asthma during the run-in period (see section VI for definition of significant exacerbation and guidelines for treatment).
2. Inability to comply with regular use of MDI (use of scheduled MDI less than twice/day on more than 12 days in the run-in period), as reflected by the diary card.
3. Failure to record peak flow measurements and symptoms in a symptom diary on average more than two days/week during the run-in period.
4. Any changes with regard to any of the exclusion criteria identified for visit 1 (see Section IIIB above).
5. Use of an average of • 16 puffs of albuterol per 24 hours during last week of run-in (week 6).
6. Prebronchodilator FEV₁ < 55% of predicted normal.

E. Criteria for Stratification into Two Subgroups (based on severity of airway obstruction and/or PEF stability) (Subgroups I and II) at Visit 5

Criteria for stratification into *Subgroup I*:

1. FEV₁ is > 80% predicted and PEF variability $\frac{PM - AM}{1/2(PM+AM)}$ in previous two weeks is ≤ 20%.

Criteria for stratification into **Subgroup II**:

1. $FEV_1 \leq 80\%$ of predicted.
2. If FEV_1 is $> 80\%$ predicted, average variability $\frac{PM-AM}{1/2(PM+AM)}$ in PEF $> 20\%$ during the previous two weeks.

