Since less-significant changes in symptoms and/or PEF may precede more severe alterations in asthma stability, a series of rescue algorithms has been developed to address the various clinical presentations that may occur (Section VI 2). Once any of these rescue interventions leads to the administration of oral or parenteral corticosteroids, the patient will also be considered to have developed a significant asthma exacerbation. In addition, if in the opinion of the treating physician, corticosteroid therapy is warranted regardless of any antecedent measurements of pulmonary function (PEF, FEV, etc.), value for symptom score, or frequency of rescue beta agonist use, the patient will be considered to have developed a significant asthma exacerbation. It should be noted that although any patient who has developed a significant asthma exacerbation will also achieve treatment failure status, it is possible that a patient may meet the criteria for treatment failure status even though he/she does not meet the criteria for having developed a significant asthma exacerbation.

The time in which a significant asthma exacerbation develops in relationship to the schedule of the SLIC protocol will affect the manner in which future clinic visits, medication adjustments, and diagnostic studies are scheduled or performed.

- Patients developing significant asthma exacerbations during the run-in period will be removed from the study. Once the exacerbation has resolved, the patient may be considered for re-enrollment, starting again at visit 1 and undergoing randomization into either SOCS or SLIC.
- Significant asthma exacerbations which occur following randomization (double-blind treatment phase) will be recorded and the patient considered a treatment failure. During medical management of the exacerbation, trial salmeterol or placebo will be continued, unless the treating physician considers it appropriate to suspend such therapy until the exacerbation resolves. Reinstitution of trial medications (salmeterol or placebo) will occur when the exacerbation has resolved at the discretion of the investigator.

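### Section VI.C drops the word significant: it ties both run-in removal and the return to open-label full-dose inhaled steroid to any exacerbation, in conflict with III.D, III.G, VI.A and VII.B

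*Protocol*

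**What the plan says.** Protocol section VI.A sets up two tiers: "An exacerbation may be brief and self-limited, or it may be of sufficient severity as to warrant documentation as a significant asthma exacerbation". Two actions then depend on which tier applies.

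**Removal from the run-in.** VI.A states: "Patients developing significant asthma exacerbations during the run-in period will be removed from the study". Section III.D, item 1, likewise excludes at Visit 4 for "Significant exacerbation of asthma during the run-in period". The second paragraph of VI.C says "Patients developing asthma exacerbation during the" run-in are to be removed, with no grade of severity.

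**Return to open-label inhaled steroid.** Section III.G, item 2, states: "If patients meet criteria for treatment failure status, their dose of inhaled corticosteroids will be increased" to the Visit 4 level of 800 µg/day, from an open-label inhaler. The texts for Visits 5 to 10 and for the Treatment Failure Visit repeat this. VI.A introduces the same switch after saying: "Significant asthma exacerbations which occur following randomization (double-blind treatment phase) will be recorded and the patient considered a treatment failure". VII.B.1 ties the return to the initial inhaled dose to an exacerbation that needed oral or parenteral steroid. VI.C states: "Trial triamcinolone or placebo will be stopped during exacerbations, and open label triamcinolone acetate", and the sentence continues "4 puffs) BID] restarted unless the treating physician considers it appropriate to suspend such therapy until the exacerbation resolves". The first paragraph of VI.C then closes by making only a significant exacerbation a treatment failure by definition.

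**The concern.** The primary outcome is time to treatment failure (section IV), and the trial asks whether inhaled steroid can be reduced and stopped under salmeterol. If a patient can be put back on the full dose by a rule wider than the failure definition, that patient stays at risk and event-free while no longer receiving the reduced-steroid strategy. In Group C this lowers the observed failure rate. In Group B it does not change the steroid dose, because the reduction there is a sham. The distortion in the primary comparison of B with C would therefore fall on one arm, and it would make withdrawal look safer.

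The run-in conflict is simpler. A patient with a minor flare is kept under III.D and VI.A and removed under VI.C, so a site cannot follow both.

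**Working it through.** **1. The triggers side by side**

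| Place | Run-in removal | Open-label inhaled steroid |
|---|---|---|
| III.D item 1 | significant exacerbation | – |
| III.G item 2, Visits 5–10, Treatment Failure Visit | – | treatment failure status |
| VI.A | significant exacerbation | stated under significant exacerbations, which are counted as failures |
| VI.C | exacerbation | exacerbation |
| VII.B.1 | – | exacerbation needing oral or parenteral steroid |

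The dose is the same throughout: 2 × 400 = 800 µg/day.

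**2. Can a switched patient be a non-failure?** The list in III.F includes oral or parenteral steroid for asthma, a significant exacerbation, peak flow, FEV1 and albuterol limits, and physician judgment. It does not include a restart of open-label inhaled steroid. A patient switched under the literal VI.C who meets none of the listed items is therefore event-free, unless the physician chooses to declare failure.

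**3. What then applies to that patient?** III.G item 1 withholds the Visit 7 reduction only for failures, and Visits 6 to 10 issue new coded steroid inhalers to patients who have not failed. VI.C describes restarting open-label drug but no return to the coded inhalers. The patient would fall under conflicting instructions.

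**4. Illustration of size.** The documents state no frequency, so the restored fraction x is an assumption.

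Inputs from section X.F: failure rates 5% (B) and 20% (C), one-sided α = 0.029, 130 patients in B and C, 10% withdrawal.

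- Plan's own figure: Δ = ln(0.80)/ln(0.95) = 4.35. Events = 4(0.842 + 1.896)²/(ln 4.35)² = 13.9. N = 13.9/0.125 = 111, or 124 after 10% withdrawal (125 if events are first rounded up to 14). The stated 130 is slightly larger. This is a separate matter.
- Power at the stated size: 130 × 0.9/2 = 58.5 per arm; d = 58.5 × (0.20 + 0.05) = 14.6 events; Φ(√(d/4) × ln Δ − 1.896) = 82%.
- Suppose a fraction x of Group C is restored halfway between Visit 5 and week 24, then carries Group B's hazard to the end. The cumulative hazards are −ln 0.95 = 0.0513 and −ln 0.80 = 0.2231. Failure in a restored patient = 1 − exp(−(0.0513 + 0.2231)/2) = 12.8%.
- Observed Group C rate = (1 − x) × 20% + x × 12.8%, with power from the same formula:

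| x (assumed) | Group C rate | Power, B versus C |
|---|---|---|
| 0 | 20% | 82% |
| 10% | 19.3% | 79% |
| 20% | 18.6% | 75% |
| 40% | 17.1% | 67% |

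Shorter restoration would give smaller effects.

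**5. C versus A.** A restored Group A patient receives inhaled steroid without salmeterol, for which section X.F assumes no rate, so no figure is given. Section V.G expects Group A to be at increased risk of exacerbation. More restoration there would lower A's failure rate and tend to shrink the difference from C. That works against the steroid-sparing conclusion.

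**The case against.** A reader might infer that the protocol requires a return to full-dose steroid for any flare, and that such patients are scored as successfully reduced. The documents do not support this.

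- VI.C nearly repeats VI.A text that sits under significant exacerbations already counted as failures, and the contents page titles section VI with the word significant.
- VI.B.1 describes albuterol for a flare that responds within 60 minutes, with no steroid switch.
- The four inhalers issued at Visit 4 include no open-label triamcinolone. Every visit text that supplies it does so on treatment failure.
- VI.C contains a physician exception.
- III.F is wide, so few patients would be ill enough to switch yet meet none of its criteria.
- The protocol has no category of successful reduction. Patients are event-free or censored.

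Most of this stands, and it makes significant the likely intent. It does not remove the conflict. The body heading of section VI omits the word significant. VI.B uses the bare term for the wider tier and reserves significant for non-response. VI.C uses both terms in one paragraph, so a coordinator has textual grounds for the literal reading. The physician exception concerns suspending therapy until resolution, after which VI.C speaks only of reinstituting open-label drug. Physician judgment under III.F is discretionary.

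Two further inferences should be resisted. Run-in removal comes before randomization and allows re-enrollment, so it may change who enters but does not bias the comparison of arms. Nor does the distortion uniformly favour withdrawal, given the opposing effect through Group A.

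**Conclusion.** The inconsistency is real and lies in the operative text. VI.C gives a wider trigger than III.D, III.G, VI.A and VII.B.1 for the same two actions, and its literal reading lets a Group A or C patient be on 800 µg/day and event-free. It is a wording conflict, not a design choice.

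The bias is conditional on sites following VI.C literally, and its size cannot be derived from the documents. The power figures rest on assumed fractions, on restoration at mid-follow-up lasting to week 24, and on Group B's hazard afterwards. At 10% restored, power is 79%, close to the planned 80%. A power loss should not be reported as a finding. The conflict stands without the figures, and the reason to correct it is that it touches the primary endpoint and eligibility at almost no cost.

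**What to change.** Reconcile VI.C with VI.A, III.D item 1, III.G item 2 and VII.B.1, so that one defined trigger governs run-in removal and one governs the switch to open-label inhaled steroid, each stated in the same words wherever it appears. The sponsor chooses the triggers; nothing here argues for a particular clinical rule.

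Then check the switch trigger against III.F and make the two agree, so that no patient switched from coded to open-label steroid for asthma is scored as event-free. If the switch trigger is treatment failure status itself, III.F needs no change.

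The cost is a few words in VI.C and VII.B.1, plus a clarification to sites. Sample size, visits and data collection are unaffected.
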